6.6 Criteria for Removal

Patients will be removed from study when any of the criteria listed in Section 6.4 applies. The reason for study removal and the date the patient was removed must be documented in source documentation and the Case Report Form. Patients continuing study treatment following unblinding by the Sponsor-Investigator will be treated as per standard of care and therefore will no longer be required to follow the study calendar or complete any of the study assessments that are not part of standard of care. Following unblinding by the Sponsor-Investigator, study teams will no longer be required to enter data into the database aside from SAEs and patient status updates (in the Screening/Enrollment tab in Velos).

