8. ADVERSE EVENTS: LIST AND REPORTING REQUIREMENTS

An Adverse Event (AE) is any undesirable sign, symptom or medical condition or experience that develops or worsens in severity after starting the first dose of study treatment or any procedure specified in the protocol, even if the event is not considered to be related to the study.

Abnormal laboratory values or diagnostic test results constitute adverse events only if they induce clinical signs or symptoms or require treatment or further diagnostic tests.

Adverse events will be monitored from the time the subject signs informed consent. Subjects will be instructed to report all AEs during the study and subjects will be assessed for the occurrence of AEs throughout the study. All AEs (serious and non-serious) must be recorded on the source documents and case report forms regardless of the assumption of a causal relationship with the study drug.

Adverse Events that begin or worsen after informed consent should be recorded in the Adverse Events section of the case report form (CRF). Conditions that were already present at the time of informed consent should be recorded in the baseline symptoms section of the CRF. Adverse Event monitoring should be continued for at least 30 days following the last dose of study treatment. Adverse Events (including lab abnormalities that constitute AEs) should be described using a diagnosis whenever possible, rather than individual underlying signs and symptoms. When a clear diagnosis cannot be identified, each sign or symptom should be reported as a separate AE.

The following list of AEs (Section 8.1) and the characteristics of an observed AE (Section 8.2) will determine whether the event requires expedited reporting **in addition** to routine reporting.

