For either continuous or intermittent dosing, the onset of neutropenia (most frequently Grade 2) occurs by Day 15, reaching a nadir in the third or fourth week with recovery during the week of drug holiday. Some patients require additional time for recovery (7 to 14 days). During this regime, growth factors are allowed.

QTc changes become evident in the first cycle by Day 8 and later (once steady state is reached), are associated with the maximum drug levels between 1 to 8 h post-dose, and remain stable or improve in subsequent cycles. Asymptomatic Grade 2 QTc prolongation was observed with increasing frequency at doses greater than 600 mg, and was considered the dose limiting toxicity. Two patients at 600 mg and two patients at 900 mg had asymptomatic QTc prolongation >500 ms (grade 3). One grade 1 atrioventricular block of first degree was reported as potentially related to ribociclib (at a dose of 140 mg). No other cardiac abnormalities were observed as related adverse events in any patient

There have been 4 deaths related to study drug reported as of April 2014. The following serious adverse events shown in the table below have been reported with a suspected causal relationship to ribociclib administration. For a complete list of AEs, all grades and Grade 3/4 that are suspected to be related to ribociclib refer to the Investigator Brochure.

Serious Adverse Events:

System Involved / Type of AE	Event(s)
Blood and lymphatic system	Anemia, febrile neutropenia, neutropenia, thrombocytopenia, Leukopenia, Lymphopenia
Gastrointestinal	Nausea, Vomiting, Diarrhea

Hepatobiliary disorders	Hepatic function abnormal Hepatocellular injury Cholecystitis
Investigations (incl. laboratory abnormalities)	Electrocardiogram QT prolonged Transaminases increased Blood creatinine increased

Severe, life-threatening, or fatal interstitial lung disease (ILD) and/or pneumonitis can occur in patients treated with KISQALI and other CDK4/6 inhibitors. Across clinical trials (MONALEESA-2, MONALEESA-3, MONALEESA-7), 1.1% of KISQALI-treated patients had ILD/pneumonitis of any grade, 0.3% had Grade 3 or 4, and 0.1% had a fatal outcome. Additional cases of ILD/pneumonitis have been observed in the postmarketing setting, with fatalities reported.

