The table below applies to Scenario 2 patients who were Actively receiving treatment when unblinded by the Sponsor-Investigator at the end of August 2023, due to the expiration and discontinuation of the Novartis manufactured placebo for this study. Guidance was provided to all study sites noting that all patients that are Active/On Treatment on scenario 2 will undergo an unblinding process following which patients will continue to receive the assigned treatment: patient who received Ribociclib will continue to do so and patients who received Placebo will continue to receive the endocrine treatment alone, as part of the study. Please note, the study does not allow for crossover between the study groups.

	Patient Visit ¹ (ongoing)
SAE ²	X
Disease Progression ³	X
Patient Status on Study ⁴	X

1. Visit frequency should be determined as per standard of care.
2. All SAEs experienced by patients receiving study treatment should be reported as per section 8.2.7 and entered in the Velos database.
3. Disease Progression should be documented in the patient statuses in velos, as reason for removal from study treatment, if applicable.
4. Any update to the patients' stua y status should be entered in Velos.

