13.3 Evaluation of Toxicity

The frequency of subjects experiencing toxicities will be tabulated.

The case report form will be utilized for AE reporting, based upon the CTEP Active Version of the NCI Common Terminology Criteria for Adverse Events (CTCAE) v4.0.

The descriptions and grading scales in CTEP Version 4.0 of the CTCAE can be located on the CTEP website at: http://ctep.cancer.gov/protocolDevelopment/electronic_applications/ctc.htm.

All patients will be evaluable for toxicity from the time of their first treatment with the investigational drug.

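### After the August 2023 unblinding only SAEs must still be entered as safety data for patients who stay on treatment, so the toxicity table in Section 13.3, which has no cut-off, mixes two collection windows

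*Combined protocol and SAP*

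**What the plan says.** **General rule.** Section 8 states: "All AEs (serious and non-serious) must be recorded on the source" documents and case report forms. It adds: "Adverse Event monitoring should be continued for at least 30 days following the last dose of study treatment". Section 8.2.7 likewise sends both AEs and SAEs to the case report forms. Section 6.5 and the second section numbered 8.2.14 (monitoring and period of observation) require serious and non-serious events within 30 days of the last study intervention to be followed. None of these makes an exception for unblinded patients.

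**Rule after unblinding.** Under Section 6.6, patients who continue treatment after the sponsor's unblinding are treated per standard of care and "will no longer be required to follow the study calendar"; study teams "will no longer be required to enter data into the database aside from SAEs" and patient status updates. Table 3 in Section 10.3 covers Scenario 2 patients on treatment at the end of August 2023. It lists SAEs, disease progression and patient status, and has no row for non-serious events. Its safety note reads: "All SAEs experienced by patients receiving study treatment should be reported as per section 8.2.7". Sections 10.3 and 13.6 say these patients continue their assigned treatment as part of the study: ribociclib in one arm, endocrine therapy alone in the other.

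**Analysis.** Section 13.3 says: "The frequency of subjects experiencing toxicities will be tabulated". The source is the case report form, and patients are evaluable from their first treatment with the investigational drug. Section 13.1 restricts safety endpoints to patients with at least one dose. Neither section gives an end date or an exposure adjustment. The comparison by arm comes from the fourth objective in Section 1.2.2, on adverse event rates and tolerability with and without ribociclib.

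**The concern.** A frequency table is interpretable only if every event in it was looked for over a stated period. Here the period depends on the kind of event. For patients unblinded on treatment, serious events are required to the end of treatment and the 30 days after it, while non-serious events are required only up to the unblinding. Nothing in Section 13.3 tells the analyst to separate the two or the reader that they differ.

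The affected patients are those treated longest, so what is at risk is the description of late, non-serious harm and tolerability. Section 7 also asks for dose changes to be recorded on a case report form, and Section 6.6 lifts that entry requirement as well. The point concerns the safety data only. It does not bear on the primary PFS analysis.

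**Working it through.** There is no planned figure to reproduce. The check is a comparison of sections, followed by an illustration of scale.

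**1. Do the sections conflict?** Sections 8, 8.2.7 and 8.2.14 cover all events to 30 days after the last dose or intervention. Sections 6.6 and 10.3 require only SAEs, progression and status for patients who are still taking study treatment, so their 30-day window has not begun. Table 3 refers sites to Section 8.2.7 for SAEs, yet that section requires AEs as well as SAEs on the forms. The conflict stands on the text.

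**2. Does it reach the table?** Yes. Section 13.3 draws on the case report form, and Section 6.6 lifts the entry requirement for that database. No cut-off removes the later period.

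**3. What can be lost?** The table counts subjects, so a patient already counted for a term is unaffected by a repeat. Only a first occurrence, or a higher grade than before, is lost. Section 8.2.8 sends grade 5 events, and grade 4 events unless expected and specifically exempted, through SAE reporting. The gap is therefore mainly non-serious grade 1-3 events.

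**4. Scale.** Let n be the patients in an arm, k the number in it still treated at unblinding, and q the chance that such a patient later has a first (or worse-grade) non-serious event of a given type.

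- Maximum under-count of the percentage for one term = k/n.
- Expected under-count = k × q/n.
- n = 60 follows from 120 randomized evaluable patients at 1:1 (Sections 1 and 6.1). The documents give neither k nor q; both ranges below are assumptions.

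| k | Maximum, k/60 | Expected, q = 0.1 to 0.5 |
|---|---|---|
| 1 | 1.7 points | 0.2 to 0.8 |
| 3 | 5.0 points | 0.5 to 2.5 |
| 5 | 8.3 points | 0.8 to 4.2 |
| 10 | 16.7 points | 1.7 to 8.3 |

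With the 66 per arm shown in Section 6.2, the maxima are 1.5, 4.5, 7.6 and 15.2 points. Within an arm, the error can only be a missed event, never an excess one.

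**5. One example.** Section 8.1 reports that "1.1% of KISQALI-treated patients had ILD/pneumonitis of any grade, 0.3% had Grade 3 or 4", and 0.1% had a fatal outcome. Taking the fatal cases as separate, 1.1 − 0.3 − 0.1 = 0.7% were grade 1-2. In an arm of 60 that is 60 × 0.007 = 0.42 patients over all treatment, before and after unblinding. For this event the expected loss is well under one patient.

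**The case against.** The strongest reply is that Sections 6.6 and 10.3 agree with each other and read as a later, specific exception after the placebo expired. Non-serious events reported once treatment is known are open to reporting bias, so leaving them out of a between-arm comparison is defensible, and Section 13.1 calls the adverse event rate exploratory. This stands as a reason to stop the comparison at unblinding. It does not excuse a table that keeps later SAEs and drops later non-serious events without saying so, nor does it put the exception into Section 8.

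Three stronger readings are tempting and are not supported.

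- **That only SAEs are recorded.** Section 6.6 lifts a requirement for database entry. It does not forbid entry or cancel source-document recording, and progression and status are still captured.
- **That the common ribociclib toxicities go uncounted.** Section 8.1 places neutropenia onset by Day 15 and QTc change from about Day 8 of the first cycle, the latter stable or improving afterwards. Except for patients then in their first cycle, most such events came under full collection. Sections 8 and 8.2.1 also exclude laboratory changes that have no clinical consequence and need no action from being adverse events at all.
- **That ribociclib harm is under-counted relative to placebo.** The reduced entry applies to both arms. More ribociclib patients would remain on treatment if the planned medians (6.5 against 3.8 months) held, but that assumes the effect under test. The documents give no accrual dates and no number still treated by arm, and only Scenario 2 patients are affected, not the whole of each arm.

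**Conclusion.** The concern holds in a limited form. The recording rules conflict, and because Section 13.3 has no cut-off, following the plan produces a table with two collection windows for patients of both arms who were unblinded on treatment. First-onset or worse-grade non-serious events after August 2023, mainly grade 1-3, can be missing. Later-onset events are the ones exposed; early neutropenia and QTc changes are mostly already in the data.

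The size is unknown. The ceiling of 1.7 to 16.7 percentage points per term rests on an assumed 1 to 10 patients still treated in an arm of 60, and the expected loss is smaller. No differential bias against or in favour of ribociclib is shown. The reason to act is that the table would be unclear about what was collected and when, and this can be corrected at almost no cost.

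**What to change.** 1. **Section 13.3.** For patients of both arms unblinded while on treatment, close the adverse event frequency table at the unblinding date. List SAEs after that date separately by arm. State that non-serious events after that date were not systematically collected, and give the number of such patients by arm. This alone removes the mixed counting.
2. **Sections 8, 6.6 and 10.3.** Make one recording rule apply: either write the exception into Section 8 (including 8.2.7 and 8.2.14), or continue entry of all adverse events to 30 days after the last dose. Keeping only selected non-serious events would add data but would not reconcile the sections.
3. **Section 6.4 against Sections 10.3 and 13.6.** Section 6.4 lists unblinding by the sponsor among the reasons treatment ends, while the other two keep these patients on assigned treatment in the study. The sections must be reconciled, because this determines when the 30-day window starts.

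**Cost.** Item 1 is analysis-plan wording. Items 2 and 3 are a short amendment, with added data entry at sites only if entry is continued. The downside is that SAEs after unblinding leave the main table and appear in a listing.

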7. DOSING DELAYS/DOSE MODIFICATIONS

For patients who do not tolerate the protocol-specified dosing schedule, dose adjustments are permitted in order to allow the patient to continue on the study. This applies both to patients in registration scenario # 1 receiving the combination of ribociclib + AI, as well as to all patients receiving fulvestrant (or exemestane) +/- ribociclib vs. placebo. These changes should be recorded on the Dosage Administration Record case

report form in a timely manner.

7.1 Letrozole and Exemestane

There is extensive clinical experience with letrozole 2.5 mg daily dosing and exemestane 25 mg daily dosing. Severe adverse events are exceedingly rare. While many patients may suffer minor adverse events including hot flushes and arthralgias/ myalgias, there is currently no established role for dose reduction to alleviate the side effects. Thus, no dose modification of letrozole or exemestane is planned in this study. Patients who do not tolerate letrozole may be switched from the generic to brand-name aromatase inhibitor with which they started (or vice versa). The toxicity profiles are similar amongst the three aromatase inhibitors (anastrozole, letrozole, and exemestane).

If the patient enrolled in scenario #1, switching to a different aromatase inhibitor (such as letrozole to anastrozole) is not allowed in combination with ribociclib. Switching from generic to brand name, or vice versa is allowed (example: letrozole and brand name femara). Patients can also switch from generic to brand name exemestane or vice versa.

7.2 Fulvestrant

There is considerable clinical experience with fulvestrant 500 mg intramuscular dosing every 4 weeks (with an initial loading dose phase), and it is generally very well tolerated, with an adverse event profile similar to AIs. As was clearly established in the CONFIRM trial, discussed in Section 2, the higher dose of fulvestrant 500 mg is more efficacious than the lower dose of 250 mg, with essentially no difference in adverse event rates. Dose reduction to 250 mg is left to the discretion of the treating physician, but it is not anticipated that dose reduction will improve adverse effects and it should generally be avoided given the inferior efficacy. In addition, dose reduction to fulvestrant 250 mg can be considered in patients with moderate hepatic impairment.

7.3 Ribociclib / Placebo

Management of severe or intolerable adverse reactions requires dose reduction, temporary interruption, and/or discontinuation of ribociclib therapy. Refer to the table below for guidance.

Dose modification guidelines: Dosing Levels

	Ribociclib/Placebo	
	Dose	Number of capsules/tablets & strength
Starting dose	600 mg	3 x 200 mg capsules/tablets
First dose reduction	400 mg	2 x 200 mg capsules/tablets
Second dose reduction	200 mg	1 x 200 mg capsules/tablets

Recommendations for dose reduction, interruption or discontinuation of ribociclib/placebo in the management of specific adverse reactions are summarized in the tables below. Definitions of grading of each Adverse Event are based on CTCAE 4.0. Clinical judgment of the treating physician should guide the management plan of each patient based on individual benefit/risk assessment.

If ribociclib is held, the cycle continues, as the patient will be taking hormone therapy. Missed doses of ribociclib will not be made up.

Subjects enrolled on Scenario 1a who are not able to tolerate ribociclib, despite dose reduction to the lowest dose (200 mg), will come off study and not be randomized to Scenario 1b.

Dose modification for hematologic adverse reactions:

LAB ABNORMALITY /	GRADE	DOSE ADJUSTMENT /
-------------------	-------	-------------------

TOXICITY		MANAGEMENT REC'S
Thrombocytopenia	Grade 1: ($\geq 75 \times 10^9/L$)	No dose adjustment required.
	Grade 2: ($\geq 50-75 \times 10^9/L$)	Dose interruption until recovery to grade ≤ 1 . Re-initiate ribociclib/placebo at the same dose.
	Grade 3: ($\geq 25-50 \times 10^9/L$)	Dose interruption until recovery to grade ≤ 1 . Re-initiate ribociclib/placebo at the same dose level. If grade 3 toxicity recurs, interrupt dose until recovery to grade ≤ 1 and then resume at next lower dose level.
	Grade 4: ($< 25 \times 10^9/L$)	Dose interruption until recovery to grade ≤ 1 . Re-initiate ribociclib/placebo at the next lower dose level. If toxicity recurs at grade 4: discontinue ribociclib/placebo.
Absolute Neutrophil Count*	Grade 1: ($\geq 1.5 \times 10^9/L$)	No dose adjustment required.
	Grade 2: ($\geq 1.0 - < 1.5 \times 10^9/L$)	No dose adjustment required.
	Grade 3: ($\geq 0.5 - < 1.0 \times 10^9/L$)	Dose interruption until recovery to $\geq 1.0 \times 10^9/L$. Re-initiate ribociclib/placebo at the same dose level. If grade 3 toxicity recurs, interrupt dose until recover to $\geq 1.0 \times 10^9/L$. If resolved in ≤ 7 days, then resume at same dose level. If resolved in > 7 days, then resume at next lower dose level.
	Grade 4: ($< 0.5 \times 10^9/L$)	Dose interruption until recovery to $\geq 1.0 \times 10^9/L$. Re-initiate ribociclib/placebo at the next lower dose level. If toxicity recurs at grade 4: temporary dose interruption until recovery to $\geq 1.0 \times 10^9/L$ and reduce ribociclib/placebo to the next lower dose level.
Febrile Neutropenia*	Grade 3: ANC $< 1.0 \times 10^9/L$ with a single temperature of > 38.3 C or a sustained temperature of ≥ 38 C for more than one hour.	Dose interruption until improvement of ANC $\geq 1.0 \times 10^9/L$ and no fever. Restart at the next lower dose level. If febrile neutropenia recurs, discontinue ribociclib/placebo.
	Grade 4: Same as grade 3, with life threatening consequences.	Discontinue ribociclib/placebo.
Anemia**	Grade 1: Hgb ≥ 10.0 gm/dL	No dose adjustment required.

	Grade 2: Hgb \geq 8.0 - < 10.0 gm/dL	No dose adjustment required.
	Grade 3: Hgb <8 gm/dL	Dose interruption until recovery to grade \leq 2. Re-initiate ribociclib/placebo at the same dose.
	Grade 4: Life-threatening consequences	Discontinue ribociclib/placebo.

* Growth factor is allowed, per investigator discretion.

** Transfusion allowed, per investigator discretion.

Dose modification for hepatic toxicity:

Hepatic toxicity monitoring includes the following LFTs: albumin, ALT, AST, total bilirubin (fractionated if total bilirubin > 2 x ULN), alkaline phosphatase, and GGT. For patients with Gilbert Syndrome: total and direct bilirubin must be monitored with intensified monitoring applying to changes in direct bilirubin only.

** TOTAL BILIRUBIN without ALT/AST increase above baseline value. ULN=upper limit of normal.	
Grade 1 (> ULN – 1.5 x ULN) (confirmed 48-72h later)	Maintain dose level. Recheck LFTs every two weeks until resolved.
Grade 2 (> 1.5 – 3.0 x ULN)	Dose interruption of ribociclib/placebo. Recheck LFTs weekly. If resolved to \leq grade 1 within 21 days, then maintain dose level. If resolved to \leq grade 1 within 21 days but toxicity recurs at grade 2, reduce 1 dose level. If resolved to \leq grade 1 > 21 days, reduce 1 dose level. Repeat liver enzyme and bilirubin tests twice weekly for 2 weeks after dose resumption If toxicity recurs after two dose reductions, discontinue ribociclib/placebo.
Grade 3 (> 3.0 – 10.0 x ULN)	Dose interruption of ribociclib/placebo. Recheck LFTs qweek. If resolved to \leq grade 1, lower 1 dose level of ribociclib/placebo. Repeat liver enzyme and bilirubin tests twice weekly for 2 weeks after dose resumption If toxicity recurs after two dose reductions, discontinue ribociclib/placebo.
Grade 4 (> 10.0 x ULN)	Discontinue ribociclib/placebo.
** Confounding factors and/or alternative causes for increase of total bilirubin should be excluded before dose interruption/reduction. They include but are not limited to: evidence of obstruction, such as elevated ALP and GGT typical of gall bladder or bile duct disease, hyperbilirubinemia due to the indirect component only (i.e. direct bilirubin component \leq 1 x ULN) due to hemolysis or Gilbert Syndrome, pharmacologic treatment, viral hepatitis, alcoholic or autoimmune hepatitis, and use of other hepatotoxic drugs. For patients with Gilbert Syndrome, these dose modifications apply to changes in direct bilirubin only.	

***AST or ALT without bilirubin elevation	
Grade 1: (>1 ULN - < 3.0x ULN).	Maintain dose level. Monitor LFTs per protocol if same grade as baseline or every two weeks in case of increase from baseline grade 0 to 1.
Grade 2: (> 3.0-≤ 5.0 x ULN)	Baseline at < Grade 2: Dose interruption of ribociclib/placebo. Recheck LFTs weekly. If resolved to ≤ baseline value within 21 days, then maintain dose level If resolved to ≤ baseline value within 21 days but toxicity recurs at same grade, then reduce 1 dose level. If resolved to ≤ grade 1 > 21 days, reduce 1 dose level. Repeat liver enzyme and bilirubin tests twice weekly for 2 weeks after dose resumption Baseline at Grade 2: Maintain dose level
Increase from baseline grade 2 to grade 3 (> 5.0 - ≤ 20.0 x ULN)	Dose interruption of ribociclib until resolved to ≤ baseline value, then lower 1 dose level of ribociclib Repeat liver enzyme and bilirubin tests twice weekly for 2 weeks after dose resumption If toxicity recurs after two dose reductions, discontinue ribociclib.
Increase from baseline grade 0 or 1 to grade 3 (> 5.0 - ≤ 20.0 x ULN)	Dose interruption of ribociclib until resolved to ≤ baseline value, then lower 1 dose level of ribociclib Repeat liver enzyme and bilirubin tests twice weekly for 2 weeks after dose resumption If toxicity recurs, discontinue ribociclib
Grade 4 (> 20.0 x ULN)	Discontinue ribociclib/placebo
AST or ALT and concurrent Bilirubin increase	
For patients with normal ALT or AST or total bilirubin at baseline : AST or ALT ≥ grade 2 combined with total bilirubin > 2 x ULN without evidence of cholestasis** OR For patient with elevated AST or ALT or total bilirubin at baseline : [AST or ALT > 2 x baseline AND > 3.0 x ULN] OR [AST or ALT 8.0 x ULN] whichever is lower combined with [total bilirubin 2xbaseline AND >2,0 x ULN]	Discontinue ribociclib/placebo
*** Confounding factors and/or alternative causes for increased transaminases should be excluded before dose interruption/reduction. They include but are not limited to: concomitant medications, herbal preparations or dietary supplements, infection, hepato-biliary disorder or obstruction, new or progressive liver metastasis, ischemic liver injury, and alcohol intake.	

Additional follow-up for hepatic toxicities

Increase in transaminases combined with total bilirubin (TBIL) increase may be indicative of drug-induced liver injury (DILI), and should be considered as clinically important events.

The threshold for potential DILI may depend on the patient's baseline AST/ALT and TBIL value; patients meeting any of the following criteria will require further follow-up as outlined below:

- For patients with normal ALT or AST or TBIL value at baseline: AST or ALT > 3.0 x ULN combined with TBIL > 2.0 x ULN
- For patients with elevated AST or ALT or TBIL value at baseline: [AST or ALT > 2 x baseline AND > 3.0 x ULN] OR [AST or ALT > 8.0 x ULN], whichever is lower, combined with [TBIL > 2 x baseline AND > 2.0 x ULN]

Medical review needs to ensure that liver test elevations are not caused by cholestasis, defined as: ALP elevation > 2.0 x ULN with R value < 2 in patients without bone metastasis, or elevation of ALP liver fraction in patients with bone metastasis.

Note: (The R value is calculated by dividing the ALT by the ALP, using multiples of the ULN for both values. It denotes the relative pattern of ALT and/or ALP elevation is due to cholestatic or hepatocellular liver injury or mixed type injury)

In the absence of cholestasis, these patients should be immediately discontinued from study drug treatment, and repeat LFT testing as soon as possible, preferably within 48 hours from the awareness of the abnormal results. The evaluation should include laboratory tests, detailed history, physical assessment and the possibility of liver metastasis or new liver lesions, obstructions/compressions, etc.

Hepatic toxicity monitoring includes the following LFTs: albumin, ALT, AST, total bilirubin, direct and indirect bilirubin, alkaline phosphatase (fractionated if alkaline phosphatase is grade 2 or higher), creatine kinase, prothrombin time (PT)/INR and GGT. For patients with Gilbert Syndrome: total and direct bilirubin must be monitored, intensified monitoring applies to changes in direct bilirubin only.

Close observation is recommended in case of AST, ALT, and/or bilirubin increase requiring dose interruption. Recommendations include:

- Repeating liver enzyme and serum bilirubin tests **two or three times weekly**. Frequency of re-testing can decrease to once a week or less if abnormalities stabilize or return to normal values.
- Obtaining a more detailed history of current symptoms.
- Obtaining a more detailed history of prior and/or concurrent diseases, including history of any pre-existing liver conditions or risk factors.
- Obtaining a history of concomitant drug use (including non-prescription medications, herbal and dietary supplements), alcohol use, recreational drug use, and special diets.
- Ruling out acute viral hepatitis types A, B, C, D, and E; hepatotropic virus infections (CMV, EBV or HSV); autoimmune or alcoholic hepatitis; NASH; hypoxic/ischemic hepatopathy; and biliary tract disease.
- Obtaining a history of exposure to environmental chemical agents.
- Obtaining additional tests to evaluate liver function, as appropriate (e.g., INR, direct bilirubin).
- Considering gastroenterology or hepatology consultations.
- Assessing cardiovascular dysfunction or impaired liver oxygenation, including hypotension or right heart failure as possible etiologies for liver dysfunction.
- Liver biopsy as clinically indicated to assess pathological change and degree of potential liver injury

Dose modification for QTc prolongation:

Grade	DOSE ADJUSTMENT / MANAGEMENT REC'S
For All Grades	
 • Check the quality of the ECG and the QT value and repeat if needed • Perform analysis of serum electrolytes (K⁺, Ca⁺⁺, Phos, Mg⁺⁺). If outside of the normal range, interrupt ribociclib administration, correct with supplements or appropriate therapy as soon as possible, and repeat electrolytes until documented as normal. • Review concomitant medication usage for the potential to inhibit CYP3A4 and/or to prolong the QT interval. • Check compliance with correct dose and administration of ribociclib.
Grade 1: QTc 450-480 ms	
 • No dose adjustment required.
Grade 2: QTc 481-500 ms	
 • Interrupt ribociclib • Perform a repeat ECG one hour after the first QTc of ≥ 481ms • If QTcF prolongation resolves to < 481 ms, resume treatment at the next lower dose level; • • If QTcF ≥ 481 ms recurs, interrupt dose until QTcF resolves to < 481 ms; then resume KISQALI at next lower dose level. • Repeat ECGs 7 days and 14 days after dose resumption (then as clinically indicated) for any patient who has therapy interrupted due to QTc ≥ 481 ms
Grade 3: QTc ≥ 501 ms on at least two separate EKGs.	
 • Interrupt ribociclib/placebo. • Consider consulting a local cardiologist • Interrupt KISQALI treatment if QTcF greater than 500 ms • Perform a repeat ECG within one hour of the first QTcF of ≥ 501ms • If QTcF remains ≥ 501ms, consult with a cardiologist (or qualified specialist) and repeat cardiac monitoring as indicated until the QTcF returns to < 481ms • If QTcF prolongation resolves to < 481 ms, resume treatment at the next lower dose level. • If QTcF remains ≥ 481 ms after performing steps 1-4 as directed in “For All Grades”, discontinue ribociclib • After resumption, EKG should be repeated 7 days and 14 days and then at least monthly. If stable at least monthly for 3 months, then can have EKG every 3 months.

	
 If QTc > 501 ms recurs, discontinue ribociclib/placebo
Grade 4: QTc ≥ 501 ms (or >60 ms increased from baseline) AND signs or symptoms of serious arrhythmias such as torsades de pointes.	Discontinue ribociclib/placebo. Obtain local cardiologist (or qualified specialist) consultation and consider repeating cardiac monitoring as indicated until the QTc returns to <481 ms.

Dose modification for ILD/pneumonitis:

Grade	Dose Adjustment and Management Recommendations
Grade 1 (asymptomatic)	No dose adjustment required..Initiate appropriate medical therapy and monitor as clinically indicated.
Grade 2 (symptomatic)	Interrupt ribociclib dose until recovery to Grade ≤1, then resume ribociclib at the next lower dose level*.
Grades 3 and 4 (severe)	Discontinue ribociclib

* An individualized benefit-risk assessment should be performed before resuming ribociclib

Dose modification for other adverse reactions:

Grade	DOSE ADJUSTMENT / MANAGEMENT REC'S
Grade 1	No dose adjustment recommended. Initiate appropriate medical therapy and monitor
Grade 2	Dose interruption until recovery to grade ≤1. Then resume at same dose level. If the same toxicity recurs at grade 2, interrupt ribociclib/placebo until recovery to grade ≤1. Re-initiate ribociclib/placebo at the next lower dose level.
Grade 3	Dose interruption until recovery to grade ≤1. Re-initiate ribociclib/placebo at the next lower dose level. If the same toxicity recurs at grade 3, re-initiate ribociclib/placebo at the next lower dose level with recovery to grade ≤1, per investigator discretion
Grade 4	Discontinue ribociclib/placebo.

7.4 Renal Impairment:

Based on pharmacokinetic/excretion studies in animals, there is minimal excretion of un-metabolized ribociclib in the urine, suggesting a limited role for renal elimination of the drug. Thus, there are currently no standard recommendations for ribociclib dose reduction based on renal impairment. Renal impairment does not affect aromatase inhibitor, such as letrozole or exemestane, or fulvestrant PK in humans (**Section 5**). Patients with baseline renal impairment are excluded from the study. Patients who develop renal impairment should be managed according to the adverse event guidelines above, including dose interruption until resolution and dose reductions for mild impairment, and withdrawal from study for more severe impairment.

7.5 Interstitial Lung Disease/Pneumonitis:

Patients receiving CDK4/6 inhibitors should be monitored for pulmonary symptoms indicative of ILD/pneumonitis which may include hypoxia, cough, and dyspnea. In patients who have new or worsening

respiratory symptoms suspected to be due to ILD or pneumonitis, interrupt treatment immediately and evaluate the patient. Treatment should be permanently discontinued in patients with recurrent symptomatic or severe ILD/pneumonitis.

